## 1.2 Study design

Figure 1 below presents the overall design of the study.

Study D1683C00008 is a 24-week, multicentre, randomised, double-blind, double-dummy, placebo-controlled, parallel-group, Phase 3 study designed to investigate if the efficacy and safety of triple combination of dapagliflozin 5 mg or 10 mg added to saxagliptin 5 mg plus metformin is superior to the dual therapy of saxagliptin 5 mg added to metformin in reducing HbA1c.

[figure not shown]
After written informed consents have been obtained at screening visit, subjects will be checked for all applicable inclusion/exclusion criteria, and laboratory samples will be taken and submitted. In Stratum A, subjects should have a stable dose of metformin immediate release (IR)/extended release (XR) ( $\geq 1500$  mg/day or a maximal tolerated dose) for at least 8 weeks prior to screening. In Stratum B, subjects should have a stable dose of metformin IR/XR ( $\geq 1500$  mg/day or a maximal tolerated dose) AND a dipeptidyl peptidase-4 (DPP-4) inhibitor (free form combination) at the maximum approved dose for at least 8 weeks prior to screening. Eligible subjects who complete the screening period will enter the lead-in period, which include open-label saxagliptin 5 mg and metformin IR/XR treatment for 16 weeks in Stratum A or 8 weeks in Stratum B. For subjects in Stratum B, DPP-4 inhibitor will be switched to saxagliptin 5 mg at Week -8. Metformin treatment regimen has to be the same as they were using at study entry and keep unchanged throughout the whole study period for both strata. On Day 1 of randomisation visit, eligible subjects will be randomised into one of three treatment groups (dapagliflozin 5 mg and dapagliflozin 10 mg placebo to match, dapagliflozin 10 mg and dapagliflozin 5 mg placebo to match, or dapagliflozin 5 mg placebo to match and dapagliflozin 10 mg placebo to match). Thereafter subjects will receive oral administration of study treatments once daily for 24 weeks. Clinic visits will be scheduled at Week 6, 12, 18 and 24 during double-blind treatment period.

Subjects with lack of glycaemic control from Week 6 up to but not including Week 24 are eligible to receive open-label rescue medication, in addition to their current double-blind treatment. All rescue decisions are based on central laboratory FPG and repeated confirmatory

FPG. It is mandatory for subjects who meet rescue criteria in the double-blind treatment period to first complete the rescue visit procedures before receiving open-label rescue medication in order to ensure important trial endpoint measurements are collected. Following completion of the rescue visit, subjects will be given open-label antidiabetic rescue medication (insulin or other antidiabetic agents except Glucagon-like peptide-1(GLP-1) analogues, other DPP-4 inhibitors and/or sodium glucose cotransporter 2 (SGLT2) inhibitors or metformin) which should be initiated at the lowest starting dose and titrated in accordance with the approved product label in the applicable country and by their glycaemic response per the investigator's judgement. Titration visit will be performed either on-site or via telephone at the discretion of the investigator. Rescued subjects then continue in the double-blind treatment period according to their original study visit schedule.

In addition, subjects who prematurely discontinue will be contacted to collect safety data.

**Figure 1 - Study Design**

### 1.3 Number of subjects

The primary endpoint (mean change from baseline in HbA1c at Week 24) will be assessed comparing dapagliflozin 5 mg or dapagliflozin 10 mg added to saxagliptin 5 mg plus metformin vs. placebo added to saxagliptin 5 mg plus metformin. Statistical significance of the primary endpoint will be claimed if the p-values for dapagliflozin 10 mg + saxagliptin 5 mg + metformin vs. placebo + saxagliptin 5 mg + metformin comparison is significant at the

2-sided, 0.05 significance level. As the success of primary endpoint on the dapagliflozin 5mg + saxagliptin 5 mg + metformin vs. placebo + saxagliptin 5 mg + metformin comparison is important, the sample size is planned to provide at least 90% power for primary endpoint on both comparisons.

With 108 subjects per treatment group with post-baseline assessment, there is 95% power to detect -0.5% difference for dapagliflozin 10mg + saxagliptin 5 mg + metformin vs. placebo + saxagliptin 5 mg + metformin comparison, assuming a standard deviation (SD) of 1.0% with a 2-sided significance level of 0.05. This sample size will also provide at least 90% power to detect -0.5% difference for both dapagliflozin 10mg + saxagliptin 5 mg + metformin vs. placebo + saxagliptin 5 mg + metformin and dapagliflozin 5mg + saxagliptin 5 mg + metformin vs. placebo + saxagliptin 5 mg + metformin comparisons, assuming a standard deviation (SD) of 1.0% with a 2-sided significance level of 0.05.

Assuming that 5% of subjects would not have a post-baseline assessment, a total of approximately 342 subjects (114 subjects per treatment arm, with about 91 subjects from China and about 23 subjects from other countries/regions) need to be randomised. In other words, subjects in China will constitute about 80% of the total number of subjects. This study includes two strata, based on prior antihyperglycemic treatment. Stratum A includes subjects whose HbA1c is uncontrolled on a stable dose of metformin and are enrolled into a 16-week open-label treatment period, adding saxagliptin 5 mg to metformin. Subjects in stratum A who remain uncontrolled are subsequently randomised. Stratum B includes subjects whose HbA1c is uncontrolled on a stable dose of metformin and a maximal dose of a DPP-4 inhibitor who are randomised following treatment with saxagliptin 5 mg during an 8-week open-label treatment period.

It is desired to have approximately 33% of the randomised subjects coming from Stratum B. In addition, Enrolment of subjects with HbA1c  $\geq 8.0\%$  and  $< 9.0\%$  (Stratum A) and subjects with HbA1c  $\geq 7.5\%$  and  $\leq 8.5\%$  (Stratum B) into the open-label treatment period will be limited to approximately 171 subjects (about 50% of the randomised subjects number in each stratum).

About 40% (Stratum A) and 6.5% (Stratum B) of subjects are expected to be discontinued due to severe lack of glycaemic control (defined as FPG  $> 270$  mg/dL at Week -10 or Week -2 in Stratum A and Week -2 only in Stratum B) during the open-label treatment period. In addition, it is expected that 50% of screened subjects will fail to meet eligible criteria for each stratum. This leads to a total of 1004 subjects to be screened, with a targeted 380 subjects in Stratum A and 122 subjects in Stratum B to enter the open-label treatment period.

## **2. ANALYSIS SETS**

### **2.1 Definition of analysis sets**

The primary efficacy analysis and exploratory analysis will be performed based on Intent-to-treat (ITT) analysis set. Safety analysis for double-blind treatment period will be performed

based on the Safety analysis set. Selected safety analyses for the open-label treatment period will be based on Open-label treated subjects analysis set.

### **2.1.1 Enrolled subjects set**

The enrolled subjects set will consist of all subjects who sign informed consent. This data set will be used to summarise the subject disposition data.

### **2.1.2 ITT analysis set**

The ITT analysis set will include all randomised subjects who received at least one dose of double-blind study medication during the double-blind treatment period. Subjects will be analysed according to the treatment groups to which they are randomised.

### **2.1.3 Per protocol (PP) analysis set**

The PP analysis set is a subset of the ITT set that includes subjects without important protocol deviations that could potentially affect the primary efficacy interpretability of the study results. Subjects will be analysed according to the treatment groups to which they are randomised. The criteria for important protocol deviations are detailed in [Section 2.2](#) below.

### **2.1.4 Safety analysis set**

The safety analysis set will include all randomised subjects who have received at least 1 dose of double-blind study medication during the double-blind treatment period. Subjects will be analysed according to treatment actually received. Subject receiving different treatment as assigned by randomisation during the entire course of study, will be analysed based on the first treatment the subject actually received.

### **2.1.5 Open-label treated subjects analysis set**

The open-label treated subjects analysis set will consist of all subjects who receive at least one dose of open-label study medication during the open-label treatment period.

## **2.2 Violations and deviations**

Important protocol deviations (IPD) are a subset of protocol deviations that may significantly impact the completeness, accuracy, and/or reliability of the study data or that may significantly affect a subject's rights, safety, or wellbeing.

A list of important protocol deviations and any action to be taken regarding the exclusion of subjects or affected data from the primary efficacy analysis are defined in appendix 1. This list will be finalised before the data has been unblinded. A report will be generated based on both IMPACT and programmatic checking results. IPDs that are determined to have the potential to affect the primary efficacy results are deemed PP Relevant IPDs. Subjects who have any PP relevant IPDs as detailed in appendix 1 will be excluded from the PP analysis set.

### **3. PRIMARY AND SECONDARY VARIABLES**

#### **3.1 General principles taken for analysis variables**

##### **3.1.1 Study Day Definition**

For the purposes of the data summaries, Study Day 1 is defined as the first dose date of study medication in each treatment period. For visits (or events) that occur on or after first dose date of study medication, study day is defined as:

(date of visit [event] – first dose date of study medication + 1).

For visits (or events) that occur prior to first dose date of study medication, study day is defined as:

(date of visit [event] - first dose date of study medication).

There is no Study Day 0.

For listings (such as for AEs/SAEs that include the derivation of “days since last dose”, this is defined as:

(event date – last treatment date of study medication).

Events that occur on the same day as the last dose of study medication will therefore be described as occurring zero days from the last dose of study medication.

##### **3.1.2 Duration of Type 2 Diabetes**

Duration of T2DM is calculated as the number of years from T2DM diagnosis date to informed consent date:

(consent date - diagnosis date +1) / 365.25.

The duration of diabetes will be included in the baseline diabetes characteristics listing.

If the date T2DM was diagnosed is partially missing, the following rules will take effect:

- Missing day, but month and year are present: the day will be imputed as the 15th day of the month.
- Missing day and month, but year is present: the day and month will be imputed as 30 June of the year (provided that the imputed date is less than the consent date).
- Missing year, but day and month are present: No imputations will occur, and the subject will be excluded from all summaries related to duration of T2DM.
- Missing day, month and year: No imputations will occur, and the subject will be excluded from all summaries related to duration of T2DM.
- If any such imputed date falls after the consent date, then the diagnosis date will be taken as equal to the consent date.

These durations, even if partially imputed, will be listed. However, only the portion of the date of diagnosis actually observed, rather than imputed dates, will be displayed in listings.

### **3.1.3      Definition of Baseline Measurements**

Unless otherwise stated, for each subject, double-blind baseline value of a parameter (e.g., efficacy laboratory parameter, safety laboratory test) is defined as the last assessment on or prior to the date of the first dose of the double-blind study medication. Open-label baseline is defined as the last assessment on or prior to the date of the first dose of the open-label medication.

### **3.1.4      Change and Percent Change from Baseline**

Change from baseline to any Week  $t$  is defined as follows:

$$C_{\text{Week } t} = M_{\text{Week } t} - M_{\text{baseline}},$$

where:

- $C_{\text{Week } t}$  is the change from baseline at Week  $t$ ,
- $M_{\text{Week } t}$  is the measurement at Week  $t$ ,
- $M_{\text{baseline}}$  is the measurement at baseline.

Percent change from baseline to any Week  $t$  is defined as follows:

$$P_{\text{Week } t} = 100 \times (M_{\text{Week } t} - M_{\text{baseline}}) / M_{\text{baseline}}.$$

Where  $P_{\text{Week } t}$  is the percent change from baseline at Week  $t$ , and  $M_{\text{Week } t}$  and  $M_{\text{baseline}}$  are defined as above.

The “Week  $t$ ” to which a measurement belongs is determined using the conventions described in section [3.1.5](#).

### **3.1.5      Visit Windows**

For summaries of vital signs and laboratory data, assessments will be assigned to calculated visit windows (using study day) as described in [Table 1](#) for double-blind treatment period and [Table 2a](#) and [Table 2b](#) for open-label treatment period below.

Inclusion within the visit window should be based on the actual date and not the intended date of the visit. The window for the visits following baseline (including unscheduled visits) will be constructed in such a way that the upper limit of the interval falls half way between the two visits.

For laboratory and non-laboratory parameters, unless otherwise specified, if a subject has more than one measurement included within a window, the assessment closest to the target day will be used. In case of ties between observations located on different sides of the target day, the earlier assessment will be used. In case of ties located on the same side of the target

day (i.e. more than one value for the same day but different time), the value with the earlier entry date/time will be used. If two non-missing values are recorded on the same day and have no assessment time associated with at least one of them, or the same assessment time associated with both of them, the average of the two values will be selected for analysis at that visit.

**Table 1 - Visit Windows for double-blind treatment period**

Assessment	Visit	Week	Target Day	Day Range
HbA1c, body weight, FPG, laboratory parameters, vital sign parameters				
Screening/Baseline	0			
Week 6	1	6	43	2-64*
Week 12	2	12	85	65-106*
Week 18	3	18	127	107-148*
Week 24	4	24	169	149-Last day of double-blind treatment + $x$ day**
MTT, ECG, Lipids, Waist circumference				
Screening/Baseline	0			
Week 24	1	24	169	2-Last day of double-blind treatment + $x$ day**

\* on or before the last day of double-blind treatment

\*\*In efficacy analysis,  $x = 8$  for HbA1c and body weight,  $x = 1$  for FPG and MTT, and  $x = 4$  for Lipids; In safety analysis,  $x = 4$  for ECG, vital signs, and laboratory data, and  $x = 30$  for liver function.

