#### 4.2.4.2 Primary efficacy outcome variable

The primary endpoint is the change in HbA1c from baseline to Week 24. The primary efficacy analysis will be based on the ITT analysis set including values prior to rescue treatment or discontinuation. Values recorded after rescue treatment or values collected more than 8 days after last dose date of the double-blind study medication are excluded from the analysis.

A mixed-model repeated-measures (MMRM) analysis using ‘direct likelihood’ will be performed. The SAS procedure PROC MIXED will be used. The preferred model will include the fixed categorical effects of treatment, stratum, time and treatment-by-time interaction as well as the continuous fixed covariates of baseline measurement and baseline measurement-by-time interaction.

The following model will be used:

$$C_{ijkm} = \text{intercept} + \beta_1 [M_{\text{baseline},ijm}] + \tau_i + s_m + \alpha_k + (\alpha \tau)_{ik} + (\alpha M_{\text{baseline}})_{ijkm} + \text{error}_{ijkm}$$

where

- $C_{ijkm}$  is the change from baseline for subject j in treatment group I of stratification group m at time k,
- $\beta_1$  is the slope coefficient for the baseline measurement,
- $M_{\text{baseline},ijm}$  is the baseline measurement of subject j in treatment group i of stratification group m,
- $\tau_i$  is the mean effect of treatment group i,
- $s_m$  is the mean effect of randomisation stratification factor group m,
- $\alpha_k$  is the mean effect at time k,
- $(\alpha \tau)_{ik}$  is the interaction term between treatment group i and time k.
- $(\alpha M_{\text{baseline}})_{ijkm}$  is baseline measurement-by-time interaction term for subject j in treatment group i of stratification group m at time k, and
- $\text{error}_{ijkm}$  is the error term for subject j in treatment group i of stratification group m at time k.

An unstructured matrix for the within-subject error variance-covariance will be used. The denominator degrees of freedom will be calculated according to the Kenward-Roger method.

In case of non-convergence of the preferred model or memory space issues, the following back-up models are defined:

- The first backup model is the same as the preferred model but the Kenward-Roger method will be replaced by Satterthwaite approximation.
- The second backup model is the same as the preferred model but the covariance matrices will be assumed in the following order Toeplitz, first-order autoregressive, compound symmetric, variance components.

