### **Sensitivity analysis**

To assess the robustness of the primary efficacy analysis for the change in HbA1c from baseline to Week 24, additional sensitivity analyses will be carried out using the following approaches:

1. A MMRM model, similar to the primary analysis, but including data after rescue and/or study treatment discontinuation, will be conducted.
2. Analysis of covariance (ANCOVA) model, with terms for treatment group, stratum, and baseline HbA1c value, including observations prior to rescue and study treatment discontinuation only, where LOCF data will be used for missing value at Week 24. The handling of LOCF is described in Section [3.1.6.1](#). The analysis will include data prior to the date of the first dose of rescue medication or up to 8 days post the last dose date of the double-blind study medication.

The following ANCOVA model will be used:

$$D_{24,ijk} = \text{Intercept} + \beta [Y_{0,ijk}] + \tau_i + s_k + \text{error}_{ijk}$$

where

- $D_{24,ijk} = Y_{24,ijk} - Y_{0,ijk}$  = the Week 24 or Week 24 LOCF change from baseline of subject  $j$  in treatment group  $i$  of stratification group  $k$ ,
- $Y_{0,ijk}$  is the baseline measurement of subject  $j$  in treatment group  $i$  of stratification group  $k$ ,
- $Y_{24,ijk}$  is the Week 24 or Week 24 LOCF measurement of subject  $j$  in treatment group  $i$  of stratification group  $k$ ,
- $\beta$  is the slope of  $D_{24,ijk}$  regressing on the baseline measurement and,
- $\tau_i$  is the mean effect of treatment group  $i$ .
- $s_k$  is the mean effect of randomisation stratification factor group  $k$ .
- $\text{Intercept}$ ,  $\beta$  and  $\tau_i$ ,  $s_k$  are unknown parameters to be estimated from the data.
- $\text{error}_{ijk}$  is the error term for subject  $j$  in treatment group  $i$  of stratification group  $k$ .

3. A MMRM model, similar to the primary analysis, using subjects in the Per Protocol Analysis Set who have a baseline assessment and any postbaseline assessment.

For each sensitivity analysis, the least squares mean estimates and 2-sided 95% confidence intervals for mean changes from baseline within and (when warranted) differences in mean change from baseline between each dapagliflozin treatment group and placebo will be provided.

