#### **4.2.4.3 Secondary efficacy variable**

##### **Mean change from baseline for FPG**

The analysis of the change from baseline for FPG at Week 24 will be performed using the same MMRM model as for the primary efficacy endpoint, as outlined in section [4.2.4.2](#), including data prior to the date of the first dose of rescue medication or up to 1 days post the last dose date of the double-blind study medication. Point estimates and 2-sided 95% confidence intervals for the mean change within each treatment group, as well as the difference in mean change between each dapagliflozin treatment group and placebo, will be calculated.

A sensitivity analysis using ANCOVA (LOCF) model, outlined in section [4.2.4.2](#), with terms for treatment group, stratum, and baseline FPG value, including observations prior to rescue and study treatment discontinuation only, will be performed.

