##### **Mean change from baseline for total body weight**

The analysis of the change from baseline for total body weight at Week 24 will be performed using the same MMRM model as for the primary efficacy endpoint, as outlined in [4.2.4.2](#), including data prior to the date of the first dose of rescue medication or up to 8 days post the last dose date of the double-blind study medication. Point estimates and 2-sided 95% confidence intervals for the mean change within each treatment group, as well as the difference in mean change between each dapagliflozin treatment group and placebo, will be calculated.

A sensitivity analysis using ANCOVA (LOCF) model, as outlined in section [4.2.4.2](#), with terms for treatment group, stratum, and baseline total body weight, including observations prior to rescue and study treatment discontinuation only, will be performed.

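### Do the Week 6, 12 and 18 windows in SAP Table 1 need the post-dose allowance that Week 24 has?

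*SAP*

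**What the plan says.** SAP Section 3.1.4 states that the week "to which a measurement belongs is determined using the conventions described in section" 3.1.5, so Table 1 decides which visit a value belongs to. For HbA1c, body weight and FPG, Table 1 gives Week 6 as Days 2-64, Week 12 as 65-106 and Week 18 as 107-148. All three carry the footnote "on or before the last day of double-blind treatment". Week 24 runs from Day 149 to last dose plus x days, with x = 8 for HbA1c and weight and x = 1 for FPG. Measures with a single post-baseline window (MTT, ECG, lipids, waist) are written "2-Last day of double-blind treatment" plus x.

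The analysis sections set their own limits:

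- **HbA1c, primary model (4.2.4.2):** "values collected more than 8 days after last dose date of the double-blind study medication are excluded from the analysis", but the sentence before it describes the data as "including values prior to rescue treatment or discontinuation".
- **HbA1c, sensitivity analysis 2 (4.2.4.2):** data before rescue "or up to 8 days post the last dose date of the double-blind study medication".
- **FPG (4.2.4.3):** "up to 1 days post the last dose date of the double-blind study medication".
- **Body weight (4.2.4.3):** "up to 8 days post the last dose date of the double-blind study medication".

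**The concern.** The MMRM in Section 4.2.4.2 has a time index, so a value without a visit cannot enter it. Take a subject who stops drug early and has the early treatment discontinuation (ETD) visit a few days later. One programmer, following Table 1, would drop that HbA1c or weight. Another, following the 8-day limit, would keep it. Because it may be the subject's last usable value, the two could get different primary estimates from the same data.

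Sensitivity analysis 1 looks worse. Its purpose is to include data after discontinuation, which Protocol Sections 3.9.3 and 4.3.3 require sites to go on collecting. With Table 1 applied unchanged, most of those data would have no window.

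**Working it through.** 1. **Reproduce the windows.** Upper limits are midpoints of the target days 43, 85, 127 and 169: (43+85)/2 = 64, (85+127)/2 = 106, (127+169)/2 = 148. These match Table 1.

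2. **Code Table 1 as written.** With L the last dose day, Week 6 = 2 to min(64, L), Week 12 = 65 to min(106, L), Week 18 = 107 to min(148, L), Week 24 = 149 to L + x.

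3. **HbA1c and weight, x = 8.** The permitted post-dose days are L+1 to L+8. For L = 1 to 140 all 8 fall on or before Day 148 and have no window: 140 × 8 = 1120. For L = 141 to 147 the number lost is 7+6+5+4+3+2+1 = 28. From L = 148 none is lost. Total 1120 + 28 = 1148, out of 169 × 8 = 1352.

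4. **FPG, x = 1.** Day L+1 has no window for L = 1 to 147, so 147 of 169.

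5. **Effect of adding x to the first three windows.** The ranges 2-64, 65-106, 107-148 and 149 onward are contiguous, so both counts fall to 0.

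6. **The literal rule is uneven.** With L = 142, HbA1c on Day 149 is Week 24 (limit 142 + 8 = 150), while HbA1c on Day 148, closer to last dose, has no visit.

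7. **Sensitivity analysis 1 read literally.** Allow later visits anywhere within 5 days of target, 11 days per visit. L = 43 leaves 33 of 33 days without a window, L = 85 leaves 22 of 22, and L = 127 leaves 11 of 11. A Day 169 sample counts only if L is at least 169 - 8 = 161.

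8. **Side effect of lengthening the windows.** Let the Week 12 visit be on Day 80, last dose on Day 84 and the ETD visit on Day 88. Table 1 as written assigns Day 80 to Week 12. With the allowance added, both days sit in Week 12. Section 3.1.5 takes the value closest to Day 85, and |88 - 85| = 3 beats |80 - 85| = 5, so the off-drug value replaces the on-treatment one.

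9. **What is still produced.** Section 4.4 keeps disposition, analysis sets, demographic and baseline tables, adverse event summaries, and listings of important deviations, observed HbA1c and marked abnormalities. Adverse events use the day rules of Section 3.5.1 and marked abnormalities those of Section 4.2.5.3. None of these outputs needs a post-baseline efficacy window from Table 1.

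**The case for a change.** The best case for a change is that the SAP gives two answers for one value in its primary model. The footnote cannot be defended as a consistent on-treatment rule, as step 6 shows. Two short lines would cure it: add the allowance to the footnote, and lift the last-dose limit for sensitivity analysis 1. The point about inconsistency stands, most clearly for FPG and weight, where the text includes post-dose data in so many words.

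Several parts are weaker:

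- **Primary HbA1c.** Protocol Section 8.5.1 and the SAP both confine this analysis to data before discontinuation, which the footnote fits. The 8-day sentence is an exclusion limit; it does not promise every earlier value a visit.
- **LOCF analyses.** SAP Section 3.1.6.1 takes the last post-baseline value before Week 24 and does not ask that it sit in a window. Sensitivity analysis 2 can therefore use the ETD value.
- **Sensitivity analysis 1.** Its one stated difference from the primary model is to admit data after rescue or discontinuation. Any analyst would let that instruction override a general on-treatment cap.
- **Single-window measures.** Lipids and the MTT have one scheduled post-baseline visit apart from rescue or ETD, so a window from Day 2 is natural there and does not show an error in the repeated-visit rows.

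Samples taken on the last dose day are never lost. In China, an ETD visit with an MTT includes dosing at the visit (Protocol Section 4.3.3). That is little comfort here, because Section 4.4 says no subjects were recruited in China. The case for no change does not rest on it.

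**Conclusion.** The wording of Table 1 and that of the analysis sections do not match for the MMRMs, and the day counts are exact. The number of subjects affected and the effect on any treatment difference cannot be derived from the documents.

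No change is called for because nothing would be gained. Section 6 drops every planned analysis except those in Section 4.4, so no MMRM, ANCOVA or by-week efficacy summary remains for the windows to alter. This rests on reading Section 6 as controlling; one sentence in Section 4.4 says loosely that planned analyses will use all available data, but the list after it contains no efficacy model. A simple extension of the windows would also carry the cost in step 8 unless on-treatment values were given precedence.

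If the models were ever run, analysts could settle the point before unblinding by applying the stated 8-day and 1-day limits at every visit, preferring an on-treatment value within a window, and using the plain day ranges for sensitivity analysis 1.
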